Cohort 1 participants confirmed to meet exclusion criterion 15 and participants who declined Year 2 IP administration will not receive their protocol-mandated glucocorticoid regimen in Year 2 and will continue receiving their background glucocorticoid treatment during Year 2, see [Appendix 12](#) and [Section 7.2.1](#).

Participants with delayed Year 2 IP administration will not receive their protocol-mandated glucocorticoid regimen until the pause is lifted and Year 2 IP administration takes place; they will remain on their background glucocorticoid regimen until then, see [Section 5.3.2](#).

Eculizumab

Treatment with one or more doses of the complement inhibitor, eculizumab, should be considered by the Investigator, according to the local prescribing information, for any participant who presents with a clinical picture of complement-mediated thrombotic microangiopathy. Signs consistent with atypical hemolytic uremic syndrome (aHUS) that would indicate the need for treatment include:

1. Creatinine $>2 \times$ Screening value; OR
2. Platelets $<75 \times 10^3/\mu\text{l}$ AND either (a) or (b):
 - a. Evidence of hemolysis:
 - Haptoglobin $<\text{LLN}$ or reduced to $<50\%$ from Screening value (Year 1) or from Visit 19 value (Year 2); or
 - Schistocytes on blood smear.
 - b. Evidence of nephropathy:
 - Anuria >12 hours; or
 - $\geq 2+$ blood or protein on urine dipstick; or
 - An increase of $>50\%$ in serum creatinine from Screening value.

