Local Laboratory Assessments

- On Visit 2 and Visits 4 to 10 (Day 2 to 10) at Year 1, and Visits 20 to 27 (Days 1 to 10) at Year 2, the sites will perform blood and urine safety tests at their local laboratories. This will ensure a very rapid turnaround (within 1 to 2 hours) and review of the results during a period that is critical for the detection of immune mediated-adverse events.
- When copies of medical records including local laboratory reports are provided to Pfizer for the purpose of critical safety review, all participant identifiers, with the exception of the participant number, must be redacted on the copies of the medical records before submission to Pfizer. The files should be password-protected.

Participants and their caregivers will be instructed to carefully monitor the liquid intake and urinary output of the participants for the first 34 days post IP administration (see [Section 5.5.2](#) for additional details). Participants will be required to return to the site for evaluation by the Investigator or designated medically qualified individual, within 24 hours if any of the following occur:

- No urine output for 12 hours, or a significant change in urine output in less than 24 hours, or observation of tea-colored urine;
- Evidence of significant reduction in estimated glomerular filtration rate, determined by clinically relevant increases in serum cystatin C or serum creatinine (eg, doubling) from value at the Screening Visit (central laboratory) or from value at the Baseline Visit (local laboratory) at Year 1 or from Visit 19 at Year 2;
- Clinically relevant increase from Screening value in hematocrit or hemoglobin;
- Presence of anion gap acidosis;
- Abnormality on blood smear, or haptoglobin <LLN or reduced to <50% from Screening value (indicating unequivocal hemolysis);
- Platelets $<75 \times 10^3/\mu\text{l}$.

Hospital admission and/or treatment with eculizumab, as per [Section 6.5.1](#), or additional immunosuppression may be warranted, at the discretion of the Investigator and/or Sponsor.

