b. To be collected pre-IP administration, and only at Year 2, Visit 20.

c. To be analyzed when possible at the site.

d. Only at Visit 8 in Year 1, and at Visit 25 in Year 2.

Note that this table only shows the local laboratory tests to be collected at these visits. For complete information, including what laboratory tests are sent to the central laboratory see [Appendix 2](#).

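### For Year 2, Sections 6.5.1 and 8.2.10 use opposite reference visits for creatinine and haptoglobin, so one creatinine result can meet one list and not the other

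*Protocol*

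**What the plan says.** Two lists in the Protocol deal with renal injury and hemolysis after dosing.

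**Section 6.5.1 (Eculizumab)** lists signs that indicate treatment for complement-mediated thrombotic microangiopathy.
- The first is creatinine above twice the "Screening value; OR". It stands alone.
- The second requires platelets below 75 x 10^3/µl together with either hemolysis or nephropathy. Haptoglobin under hemolysis is compared "from Screening value (Year 1) or from Visit 19 value (Year 2"). The creatinine item under nephropathy is a rise of more than 50% "in serum creatinine from Screening value".

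**Section 8.2.10 (Post IP Intensified Safety Monitoring)** lists events that require a return to the site within 24 hours.
- A clinically relevant rise in cystatin C or creatinine, with doubling as an example, is measured from the central-laboratory Screening value or "from value at the Baseline Visit (local laboratory) at Year 1 or from Visit 19 at Year 2".
- Haptoglobin counts if it is below the lower limit of normal (LLN) or "reduced to <50% from Screening value (indicating unequivocal hemolysis").
- Platelets below 75 x 10^3/µl are a trigger in their own right.

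Both lists apply in Year 2. Section 8.2.10 covers the first 34 days after dosing in each year, and Section 6.5.1 requires eculizumab to be on hand for two months after each dose. Section 8.2.10 refers the eculizumab decision to Section 6.5.1.

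In Section 8.2.12, note b to Table 2 adds a local creatinine at Visit 20: "To be collected pre-IP administration, and only at Year 2, Visit 20". Neither list names this value as a reference.

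**The concern.** Each section moves the reference forward to Visit 19 for one analyte and leaves the other at Screening, and they choose opposite analytes. No rule stated in the Protocol explains that pattern. It reads as two lists updated separately for Year 2.

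Year 2 is when Cohort 2 receives the active vector. Section 2.2.6 reports two serious events consistent with atypical hemolytic uremic syndrome among six high-dose Phase 1b participants, and Section 4.3 calls the present dose approximately equivalent to that one. These lists tell the site when to recall a child and when to consider treatment. At stake is whether the two steps work from the same measure of change, above all for creatinine, which is sufficient alone in Section 6.5.1.

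**Working it through.** **Side by side, Year 2 reference visit**

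| Analyte | Section 6.5.1 | Section 8.2.10 |
|---|---|---|
| Creatinine, stand-alone (more than 2 x) | Screening | Visit 19 (doubling as example; cystatin C is an alternative marker) |
| Creatinine, rise above 50% (only with low platelets) | Screening | no counterpart |
| Haptoglobin, below 50% | Visit 19 | Screening |

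Both haptoglobin references exist: note b to Table 3 (Appendix 2) schedules the test at Screening and at Visit 19.

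**Thresholds.** The plan gives no figure to reproduce. Let S be the Screening value and r the ratio of the Visit 19 value to S.
- Creatinine: 6.5.1 gives 2 x S; doubling under 8.2.10 gives 2 x r x S.
- Haptoglobin: 6.5.1 gives 0.5 x r x S; 8.2.10 gives 0.5 x S.

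The Protocol does not give r, so a range is assumed.

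| r (assumed) | Creatinine 6.5.1 | Creatinine 8.2.10 | Haptoglobin 6.5.1 | Haptoglobin 8.2.10 |
|---|---|---|---|---|
| 0.8 | 2.00 S | 1.60 S | 0.400 S | 0.500 S |
| 1.0 | 2.00 S | 2.00 S | 0.500 S | 0.500 S |
| 1.25 | 2.00 S | 2.50 S | 0.625 S | 0.500 S |
| 1.5 | 2.00 S | 3.00 S | 0.750 S | 0.500 S |

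The lists agree only at r = 1. The schedule puts Screening at Day -90 to -30 and Visit 19 at Day 360, roughly 390 to 450 days apart, so equality cannot be taken for granted.

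**Creatinine example (assumed values).** Screening 0.20, Visit 19 0.25, Year 2 result 0.45 mg/dL.
- 0.45 / 0.20 = 2.25, above 2: meets 6.5.1.
- 0.45 / 0.25 = 1.80, below 2: not a doubling under 8.2.10.

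With the two reference values swapped (Screening 0.25, Visit 19 0.20), the ratios are 1.80 and 2.25, and the disagreement reverses.

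**Haptoglobin example (assumed values, LLN assumed below 60).** Screening 100, Visit 19 140, Year 2 result 60 mg/dL.
- 60 / 140 = 43%: below half under 6.5.1.
- 60 / 100 = 60%: not below half under 8.2.10.

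**Laboratory.** For Year 1, Section 8.2.10 pairs Screening with the central laboratory and Baseline with the local one. For Year 2 it says only "local laboratory) at Year 1 or from Visit 19 at Year 2": the laboratory is named for Year 1 and not for Visit 19. Creatinine is measured locally at Visit 20 and on Days 391 and 393 (Section 8.2.12). On those two days the chemistry panel also goes to the central laboratory outside Japan (Table 3). Results from both laboratories can therefore exist for the same day.

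**The case against.** The strongest reply is that the two lists do different jobs in sequence. Section 8.2.10 brings the child back for evaluation; Section 6.5.1 then guides treatment. One site uses both, so the criteria need not be identical. Doubling is only an example in 8.2.10, and the 6.5.1 decision is left to the investigator. In Year 2, participants are also inpatients for at least 7 days and stay near the site through Day 14, so a return-to-site trigger adds little in that window. All of this is fair and limits the practical effect. It does not explain why the reference visit moves for creatinine in one list and for haptoglobin in the other.

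The haptoglobin half is rightly discounted. A value below LLN counts in both sections: 8.2.10 reads "haptoglobin <LLN or reduced to <50% from Screening value (indicating unequivocal hemolysis"). In 6.5.1 haptoglobin matters only with platelets below 75 x 10^3/µl, which already triggers 8.2.10.

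A reader might infer more than the Protocol supports:
- *That Cohort 1 and Cohort 2 safety data become non-comparable, or that the safety tables are affected.* No text carries these triggers into a table. Section 9.4.2 summarizes Cohort 2 delayed-treatment safety against its own pre-treatment baseline.
- *That normal drift could meet the 50% creatinine sign before dosing.* With 0.20 at Screening and 0.30 at Visit 19 (assumed values), the rise is exactly 50%; the sign needs more than 50% and also low platelets.
- *That all results on Days 391 to 399 are local.* Table 3 also sends the Days 391 and 393 panels to the central laboratory outside Japan.
- *That leaving the Visit 20 creatinine unused is an error.* Collecting it contradicts nothing; the Protocol just does not say whether it is a reference.

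**Conclusion.** The contradiction is real in the current text but narrow. For Year 2 the two sections give opposite reference visits for the same two analytes. It is sharpest for the stand-alone creatinine sign, where a result can meet 6.5.1 without being a doubling under 8.2.10, or the reverse. Over an assumed Visit 19 to Screening ratio of 0.8 to 1.5, doubling under 8.2.10 falls at 1.6 to 3.0 times Screening, against a fixed 2.0 under 6.5.1. The size rests on that assumed range and on using doubling as the working example; the crossing itself rests on neither. The Year 2 laboratory is a smaller gap in the same sentence of 8.2.10. Endpoints, estimands, power and alpha are untouched.

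**What to change.** Reconcile Sections 6.5.1 and 8.2.10 so that each analyte (creatinine, cystatin C where used, haptoglobin) has one stated Year 2 reference visit and one stated laboratory, worded the same way in both sections. State whether the local Visit 20 creatinine serves as a reference. Which visit and laboratory are right is a clinical decision for the sponsor; none is proposed here. The candidate samples are already scheduled (haptoglobin at Screening and Visit 19; creatinine at Screening, Visit 19 and Visit 20), so the cost is amendment wording and informing the sites.

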In order to ensure an adequate understanding and management of potential safety risks, the initial rate of randomization into the study will be limited. No more than 2 participants per week will be randomized at the start of the study, until 4 participants have been observed for at least 2 weeks post-IP administration. After that, the rate could be increased to no more than 3 participants randomized per week (until a total of 10 participants have been observed for at least 2 weeks post-IP administration). Thereafter, the rate of randomization could be further increased to no more than 5 participants randomized per week (until a total of 20 participants have been observed for at least 2 weeks post-IP administration). After this time, no limits to the randomization rate will be imposed unless the study team, in consultation with the E-DMC, determines otherwise. Ongoing blinded review of safety data will be conducted by the study team, and frequent periodic unblinded reviews of safety data will be conducted by the E-DMC, as described in detail in the E-DMC charter (see [Section 9.5.1](#)).

[Table 1](#) provides a brief overview of the study periods; for full details please see [SoA](#).

Table 1. Brief Overview of the Study Periods

Study Period	Days and Visits	Overview of Main Tests/Procedures
Study Eligibility Assessment	Screening (Visit 1)	Inclusion and Exclusion criteria review.
	Baseline (Visit 2)	Inclusion and Exclusion criteria review, including NAb results; Efficacy assessments; Muscle biopsy;* Obtain weight measurement; Randomization and request IP.
IP Administration	Day 1 (Visit 3)	Pre-dose Inclusion and Exclusion criteria review, including NAb results; Year 1 IP administration;
Post IP safety monitoring	Day 2 (Visit 4) to Day 34 (Visit 13)	Post-dose safety monitoring; Viral vector shedding.
Completion of Year 1	Day 60 (Visit 14) to Day 360 (Visit 19)	Routine safety monitoring; Efficacy assessments; Muscle biopsy (Day 360);* Obtain weight measurement (Visit 18);** Request IP on Day 328 (Visit 18); Viral vector shedding.
Eligibility Assessment for Year 2 IP Administration	Day 360 (Visit 19)	Assess eligibility for Year 2 IP administration, including NAb results. Viral vector shedding.
IP Administration	Day 390 (Visit 20)	Pre-dose review of eligibility for Year 2 IP administration, including NAb results; Year 2 IP administration.
Post IP safety monitoring	Day 391 (Visit 21) to Day 423 (Visit 30)	Post-dose safety monitoring; Viral vector shedding.

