 - a. Absolute neutrophil count <1000 cells/mm³;
 - b. Platelets <150 x 10³/μl;
 - c. Cystatin C >1.2 x ULN;
 - d. Positive hepatitis A virus (anti-HAV) immunoglobulin M, hepatitis B surface antigen (HbsAg), and/or hepatitis C antibody (HCVAb);

e. Markers of hepatic inflammation or overt or occult cirrhosis as evidenced by one or more of the following:

1. Prothrombin time (PT) > upper limit of normal (ULN); prolonged international normalized ratio (INR) >ULN;
2. GLDH >2 x ULN;
3. Total bilirubin >1.5 x ULN (unless the participant has a history of Gilbert disease) and direct bilirubin >0.5 mg/dL;
4. Gamma-glutamyl transferase (GGT) >1.5 x ULN.

9. Other acute or chronic medical or psychiatric condition at Screening (Visit 1), including recent (within the past year) or active suicidal ideation or behavior (using screening by the Child Behavior Check List (CBCL) and determined by the Investigator, as described in [Section 8.2.13](#)) or laboratory abnormality that may increase the risk associated with study participation or IP administration or may interfere with the interpretation of study results and, in the judgment of the Investigator, would make the participant inappropriate for entry into this study.

10. Acute infection at Screening (Visit 1) or Baseline (Visit 2) that, in the judgement of the Investigator is not expected to be fully resolved at least 2 weeks before Day 1 (Visit 3). At Day 1 (Visit 3), participants must have been infection-free for at least 2 weeks prior to IP administration. Delay of IP administration for up to 14 days is permitted to enable infections to become fully resolved.

11. Investigator site staff members directly involved in the conduct of the study and their family members, site staff members otherwise supervised by the Investigator, or Pfizer employees, including their family members, directly involved in the conduct of the study.

12. Known hypersensitivity to any of the components of the IP or solution for infusion, such as hypersensitivity to albumin or a diagnosis of HFI. Symptoms suggestive of HFI include nausea, vomiting, bloating, stomach cramps, or diarrhea following the ingestion of sweet foods or drinks, or a pattern of avoiding sweet foods or drinks.

13. Contraindication to the use of eculizumab, as per the local prescribing information.

14. LVEF <50% on echocardiogram performed at the Screening Visit (Visit 1), as evaluated by the central reader.

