6.1. Study Intervention(s) Administered

Intervention Name	fordadistrogene movaparvovec	Placebo for fordadistrogene movaparvovec
Type	Gene Therapy	Placebo for Gene Therapy
Use	Experimental	Placebo
IMP and NIMP/AxMP	IMP	IMP
Dose Formulation	Sterile Solution for Infusion	Sterile Solution for Infusion
Unit Dose Strength(s)	1E14 vg/mL Note: This is the nominal concentration of the IP; for lot specific dosing calculation, the exact strength of each lot will be provided. For nominal dosing, 1E14 vg/mL will be the concentration used for the calculation of the administered dose. Nominal dosing will only be implemented for Year 2 IP administration. The Sponsor will communicate to the sites what dosing strategy must be implemented for each participant to be dosed. (Refer to IP Manual for further details)	0 vg/mL
Dosage Level(s)	2E14 vg/kg Single dose IV infusion	0 vg/kg Single dose IV infusion
Route of Administration	Intravenous Infusion	Intravenous Infusion
Sourcing	Provided centrally by the Sponsor (Refer to IP Manual for further details)	Provided centrally by Sponsor (Refer to IP Manual for further details)
Packaging and Labeling	Study intervention will be provided as 5 mL per vial (5 mL/vial). Each vial will be labeled as required per country requirement	Study intervention will be provided as 5 mL per vial (5 mL/vial). Each vial will be labeled as required per country requirement
SRSD	IB	IB

Study Intervention(s)						
Intervention Name	IV methylprednisolone	Oral prednisone or prednisolone	Deflazacort	Eculizumab	Antiemetics eg. ondansetron	MenACWY Vaccine
Type	Drug	Drug	Drug	Drug	Drug	Vaccine
Use	One-time, pre-administration of IP, Year 1 and Year 2	Background glucocorticoid regimen pre- IP administration and after completion of 90-day Protocol-mandated glucocorticoid regimen for at least the first 2 years in the study. Protocol-mandated post-IP dosing for 90 days	Background glucocorticoid regimen pre- IP administration and after completion of 90-day Protocol-mandated glucocorticoid regimen for at least the first 2 years in the study	Medication to treat adverse events (aHUS), to be administered at the discretion of the Investigator. Guidance for use provided in Section 6.5.1	Medication to prevent or treat adverse events (nausea and/or vomiting), to be administered at discretion of Investigator. See Section 6.5.1	Required per eculizumab label. Must be administered no later than 30 days before and only after 60 post- IP administration. See Section 6.5.1

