Because the use of eculizumab increases the risk of contracting serious meningococcal infections, participants who have no contraindications and who have not previously received a vaccination against meningococcus or whose last vaccination at the time of the Screening Visit (Visit 1) is outside the time period of active coverage specified by the vaccine manufacturer must receive at least one dose of meningococcal conjugate (MenACWY) vaccine as early as possible in the Screening Period and not later than 30 days before IP administration. If they receive eculizumab, and depending on the duration of the treatment with eculizumab, a decision will be made as to whether they should receive a second dose of meningococcal vaccination or antibiotic prophylaxis, at the discretion of the Investigator. Participants must also receive serogroup B meningococcal (MenB) vaccination if indicated by national vaccination guidelines. The Investigator must evaluate the immunization status against meningococcus and any other locally required immunization for all participants at Screening (Visit 1); local eculizumab prescribing information, including additional vaccination, and other requirements must also be followed as needed. Additionally, all sites must have the MenACWY vaccine, MenB vaccine (if recommended in the national vaccination guidelines) and eculizumab available for all participants (eculizumab should be available for the first 2 months after IP administration at Year 1 and at Year 2). For participants who cannot receive meningococcal vaccination, antibiotic coverage must be provided simultaneously with eculizumab.

Participants who experience an event compatible with aHUS may be screened for a genetic predisposition to aHUS, as determined by the Investigator in consultation with the Sponsor to increase the understanding of the risk of developing aHUS (see [Appendix 2](#)).

Antiemetics

At the discretion of the Investigator, participants may be administered an oral antiemetic such as oral ondansetron following IP administration and following the local prescribing information to prevent or treat symptoms of nausea and vomiting. Participants (and/or caregivers) should be instructed to contact the site if vomiting continues despite anti-emetic treatment. If required, an IV antiemetic such as ondansetron may be administered by the site.

Anesthesia

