1. Positive test for NAb to AAV9, based on the threshold determined by the Central Laboratory, at Day 360 (Visit 19). If the time between Day 360 (Visit 19) and Day 390 (Visit 20) is more than 55 days, a second NAb to AAV9 test must be performed and confirmed to be negative before Year 2 IP administration. Dosing cannot occur unless there is a negative NAb to AAV9 test from a sample collected 55 or less days before the day of IP administration, as reviewed by the unblinded medical monitor.
2. Abnormality in hematology or chemistry profiles at Day 360 (Visit 19). A single repeat for value(s) outside allowable limits is permitted to re-assess eligibility:
 - Absolute neutrophil count <1000 cells/mm³;
 - Platelets <150 x 10³/μl;
 - Cystatin C >1.2 x ULN;

Positive hepatitis A virus (anti-HAV) immunoglobulin M, hepatitis B surface antigen (HbsAg), and/or hepatitis C antibody (HCVAb);

Markers of hepatic inflammation or overt or occult cirrhosis as evidenced by one or more of the following:

 - PT > ULN; prolonged INR >ULN;
 - GLDH >2 x ULN;
 - Total bilirubin >1.5 x ULN (unless the participant has a history of Gilbert disease) and direct bilirubin >0.5 mg/dL;
 - GGT >1.5 x ULN.

Additionally, the unblinded medical monitor will confirm the treatment allocation for participants with the conditions listed below, so those participants in Cohort 2 who meet any of these conditions do not receive Year 2 IP administration and are withdrawn from the study:

3. Participants screened or randomized who had not yet received Year 2 IP administration and were retrospectively confirmed to meet exclusion criterion 15 (see [Appendix 12](#)).
4. LVEF <50% on echocardiogram performed at Day 360 (Visit 19), or at the unplanned visit to re-assess eligibility for Year 2 IP administration.

5. Diagnosis of current or prior myocarditis by a pediatric cardiologist.
6. Not a candidate for mechanical cardiac or respiratory support, or any other invasive intervention, if indicated for management of an acute event as determined by the cardiologist in consultation with the investigator.

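### Neither eculizumab contraindication nor meningococcal coverage is re-checked before Year 2 dosing, when Cohort 2 first receives the vector

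*Protocol*

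**What the plan says.** **At entry.** Section 5.2, exclusion 13, bars a boy with "Contraindication to the use of eculizumab, as per the local prescribing information". Section 6.5.1 requires at least one MenACWY dose, no later than 30 days before IP, for boys without contraindications who were never vaccinated or "whose last vaccination at the time of the Screening Visit (Visit 1) is outside the time period of active coverage". It also has the investigator evaluate immunization status at Screening. The Year 1 schedule (1.3.1) marks the vaccine at Screening and Baseline only, and the Baseline mark is a catch-up for boys not vaccinated at Screening. Table 1 (Section 4.1) adds a review of the inclusion and exclusion criteria on Day 1 before dosing.

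**At Year 2.** For Day 390, Table 1 asks instead for "Pre-dose review of eligibility for Year 2 IP administration, including NAb results". The schedule (1.3.2) refers that review to Section 7.1. None of items 1 to 12 there mentions eculizumab contraindication or current meningococcal coverage. Item 6 does carry forward a closely related criterion: "Not a candidate for mechanical cardiac or respiratory support, or any other invasive intervention, if indicated for management of an acute event". The Year 2 schedule has no vaccine row.

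**Rules that soften this.** Section 6.5.1 says that "local eculizumab prescribing information, including additional vaccination, and other requirements must also be followed as needed". It requires sites to hold the vaccine, and to have eculizumab available for two months after IP in both years. It leaves a second vaccine dose or antibiotic prophylaxis to the investigator once eculizumab is given, and adds: "For participants who cannot receive meningococcal vaccination, antibiotic coverage must be provided simultaneously with eculizumab". The MenACWY entry in Section 6.1 reads "Must be administered no later than 30 days before and only after 60 post- IP administration". Section 8 has immediate safety concerns discussed with the sponsor, to decide whether study intervention continues.

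**The concern.** Exclusion 13 and the vaccination rule exist so that a boy who develops complement-mediated thrombotic microangiopathy after the vector can be given eculizumab safely. Section 2.2.6 reports two such serious events among six boys at the high Phase 1b dose, both within two weeks of infusion, and Section 4.3 calls the Phase 3 dose approximately equivalent to that dose.

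In Cohort 1 the vector comes at Day 1, soon after both checks. In Cohort 2 Day 1 is placebo and the vector comes at Day 390, so the checks sit next to the wrong dose. A site that follows the Year 2 list exactly could give the vector to a boy whose coverage has run out since Screening, or who has since become unable to receive eculizumab. What is at stake is participant safety in Cohort 2 after Week 52.

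**Working it through.** The protocol states no interval to reproduce. The check compares the entry and Year 2 lists, then works out the timing from the visit schedule.

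**Entry criteria (5.2) against Year 2 criteria (7.1)**

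- Exclusion 6, antibodies to AAV9: item 1
- Exclusion 8, hematology and chemistry: item 2
- Exclusion 15, dystrophin mutations: item 3
- Exclusion 14, LVEF: item 4
- Exclusion 16a, myocarditis: item 5
- Exclusion 17, candidacy for mechanical support: item 6
- Exclusion 13, eculizumab contraindication: no item
- Meningococcal coverage (6.5.1): no item. Item 8 asks only whether an inactivated vaccine was given too recently, not whether coverage is current.

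Exclusion 12 (hypersensitivity to IP components) has no counterpart either, so the accurate statement is that several entry safety criteria are carried forward, not all.

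**Delayed dosing.** Section 5.3 speaks generally of re-confirming eligibility when the gap exceeds 90 days. Section 5.3.2 carries this out as the Visit 19 tests plus the Section 7.1 criteria, so it adds neither check.

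**Age of the Screening check at the first vector dose.** Inputs: Screening on Day -90 to -30; Cohort 1 vector on Day 1; Cohort 2 vector on Day 390 ± 3. Formula: dosing day minus Screening day.

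- Cohort 1: 1 + 30 = 31 to 1 + 90 = 91 days
- Cohort 2: 390 + 30 = 420 to 390 + 90 = 480 days
- Cohort 2 with the ± 3-day window: 387 + 30 = 417 to 393 + 90 = 483 days
- Cohort 2, pause reaching the Day 540 monitoring visit: 540 + 30 = 570 to 540 + 90 = 630 days, with dosing later still

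If the calendar has no Day 0, the Cohort 1 and Cohort 2 figures each fall by one day.

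**Does a review at Visit 18 leave time for a booster?** Visit 18 is Day 328 ± 14, so Day 314 to 342. Section 6.5.1 allows inactivated vaccine from Day 60 to Day 360, and item 8 requires 30 days between vaccine and IP.

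- Time left to Day 360: 360 - 342 = 18 to 360 - 314 = 46 days
- Visit 20 at its early edge, Day 387: booster due by 387 - 30 = Day 357, leaving 357 - 342 = 15 to 357 - 314 = 43 days

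The ordinary case therefore fits the existing rules.

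**If a lapse is found later.** Vaccine on Day 361 to 390 puts dosing at 361 + 30 = Day 391 to 390 + 30 = Day 420, which is 1 to 30 days late. Section 6.5.1 does not at present allow an inactivated vaccine between Day 360 and Day 450, so this route needs explicit permission.

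**The case against.** **Eculizumab risk is also managed when the drug is used.** Treatment follows the local label, vaccine and eculizumab are on site, and boys who cannot be vaccinated must have antibiotics. An investigator who learns of a new contraindication can take it to the sponsor under Section 8. This stands and lowers the risk. But each of these either acts after the vector has been given or depends on someone happening to know, and antibiotics are mandatory only for boys who cannot be vaccinated, not for a boy whose coverage has lapsed. The label duty in 6.5.1 has no date, and the Section 6.1 entry governs timing without prompting a review.

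**The harm is not demonstrated.** The manufacturer's coverage period and the local labels are outside the protocol. A boy vaccinated during screening would lapse before Day 390 only if coverage lasts less than about 420 to 480 days. Otherwise the concern is confined to boys whose existing coverage was due to expire in that interval. No particular contraindication is known to arise after entry. This stands and limits the point to a missing check.

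**A conflict between the vaccine windows and item 8.** A reader might infer that item 8 contradicts 6.5.1, because it provides for a vaccine within 30 days of Day 390 when 6.5.1 allows none after Day 360. The text does not support that. Item 8 permits nothing; it says what to do if a vaccine has been given. Year 1 pairs a permitted window in 6.5.1 with the same kind of delay rule in 6.1.1, item 6. The drafting is consistent.

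**Conclusion.** The gap is real. Section 7.1 omits exclusion 13 while keeping a parallel criterion on fitness for rescue (item 6), and 6.5.1 fixes meningococcal coverage at Screening, about 420 to 480 days before Cohort 2 first receives the vector and longer after a pause. The softening rules set no check before the Year 2 dose. The point should be corrected, mainly because the remedy is cheap and concerns participant safety. Confidence is medium, since the number of boys affected is unknown.

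Two stronger readings go too far. A reader might take the interval as evidence that coverage lapses; it is only the age of the check. A reader might also expect an effect on the efficacy result; Year 2 dosing follows the Week 52 assessment, so the primary comparison is untouched.

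The intervals assume the scheduled visit days and windows.

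**What to change.** 1. **Coverage.** Review meningococcal coverage in both cohorts at Visit 18 (Day 328), so that any booster is given by Day 360 and at least 30 days before Year 2 IP. If a lapse is found later, or during a pause, state in 6.5.1 that the vaccine is permitted and delay IP by 30 days under item 8.
2. **Contraindication.** Add current eculizumab contraindication to the Year 2 criteria in Section 7.1, handled through the unblinded medical monitor. Delay IP if it is temporary. Withhold the vector from a Cohort 2 boy only if it is lasting; a Cohort 1 boy keeps his Year 2 placebo. Copying the handling of items 3 to 6 unchanged would withdraw Cohort 2 boys even for a temporary contraindication. The sponsor's clinicians should define temporary and lasting.
3. **Pauses.** Repeat both checks after any pause. The coverage review should come before the eligibility visit, because Section 5.3.2 expects dosing within 30 days of that visit while a vaccine must be at least 30 days old.

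The cost is one record review at a visit that may already be remote, one added criterion and one vaccine permission. Some boys would be dosed up to about 30 days late. With Visit 19 on Day 360, dosing after 360 + 55 = Day 415 would also need a fresh antibody test under item 1. Rarely, a Cohort 2 boy with a lasting contraindication would not receive the vector and, unless the withdrawal rule in Section 7.2 is changed, would leave the study.
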